#### 7.1.4. Pharmacokinetic Population (PK)

The PK population will consist of the subjects who were randomized, dosed, and have at least one PK value. It is planned that plasma concentration will be measured in a subset of 40 subjects. Subjects who are members of the PK population will be analyzed as treated.

## 7.2. Covariates and Subgroups

### 7.2.1. Planned Covariates

Planned covariates include baseline IOP for the efficacy analyses.

### 7.2.2. Planned Subgroups

There are no planned subgroup analyses.

## 7.3. Management of Analysis Data

### 7.3.1. Data Handling

At least one eye must qualify for the study. Even if only one eye meets all inclusion/exclusion criteria, both eyes will be treated. If both eyes qualify, the qualifying eye with the higher IOP

at 8:00 AM at Visit 3/Qualification/Baseline will be designated as the study eye. Should the 8:00 AM IOP be the same in both eyes, then the right eye will be designated as the study eye.

At each IOP measurement time point, 2 consecutive IOP measurements of each eye will be performed. If the 2 measurements differ by more than 2 mm Hg, a third measurement will be taken. Mean IOP is calculated as the mean of 2 measurements or as the median of 3 measurements.

### **7.3.2. Missing Data**

All data recorded on the electronic case report form (eCRF) will be included in data listings that will accompany the clinical study report. All efficacy analyses will be based on observed cases (without imputation). Multiple imputation methods and single imputation methods (e.g., last observation carried forward [LOCF]) will be utilized for sensitivity analyses for select variables.

#### **7.3.2.1. Handling of Missing Date Values**

##### **Partial or Missing Dates**

The following conventions will be used to impute missing portions of dates for AEs and concomitant medications, if warranted. Note that the imputed values outlined here may not always provide the most conservative date. In those circumstances, the imputed value may be replaced by a date that will lead to a more conservative analysis.

###### **A. Start Dates**

- 1) If the year is unknown, then the date will not be imputed and will be assigned a missing value.
- 2) If the month is unknown, then:
  - i) If the year matches the first dose date year, then impute the month and day of the first dose date.
  - ii) Otherwise, assign 'January.'
- 3) If the day is unknown, then:
  - i) If the month and year match the first dose date month and year, then impute the day of the first dose date.
  - ii) Otherwise, assign the first day of the month.

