9.1.2. Concomitant Medications History

All concomitant medications (prescription and over-the-counter [OTC]) taken at Visit 1/Screening and for 90 days prior to Visit 1 and throughout the course of the study will be recorded in the Concomitant Medications page of the eCRF. Information regarding the dates of first and last dose, site of dosing (e.g., right eye, left eye, both eyes [OU], systemic), and the reason the concomitant medication is being taken must be recorded in the eCRF. When a concomitant medication has been taken at a stable dose for longer than 6 months, an estimation of the year of the start date is adequate. Standard procedural medications will not be captured in the eCRF but are recorded on a standard procedural medication log provided by the CRO.

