#### **8.5. Prior and Concomitant Medications**

The number and percentages of all ocular concomitant medications will be summarized by study/non-study eye and treatment group, Anatomical Therapeutic Chemical (ATC) level 2, and PT. The total number of concomitant medications and the number and percentages of subjects with at least 1 concomitant medication will be summarized by treatment group. All summaries will be performed using the Safety Population.

A concomitant medication is defined as any medication taken on or after the day of first exposure to study drug up until 7 days after last dose of study drug.

Prior medications are defined as any medications started and stopped prior to the day of first exposure to any study drug.

Non-ocular medications will be summarized similarly.

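### The start-date imputation ignores a known stop date, so a washed-out drug or an AE that resolved before dosing can be given a start on Day 1

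*SAP*

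**What the plan says.** SAP 7.3.2.1 A gives the start-date rules. When the month is unknown: "If the year matches the first dose date year, then impute the month and day of the first dose date". If the year differs, the start goes to January. Rule A.3 does the same for an unknown day: the first-dose day if month and year match, otherwise the first of the month. The stop-date rules in part B assign December or the last day of the month. Neither part compares start with stop.

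The preamble to these rules limits them in two ways. The "conventions will be used to impute missing portions of dates for AEs and concomitant medications, if warranted". It also admits that an imputed date may not be the most conservative one: "In those circumstances, the imputed value may be replaced by a date that will lead to a more conservative analysis".

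Protocol 9.1.2 makes year-only starts an expected form of data. For a drug "taken at a stable dose for longer than 6 months, an estimation of the year of the start date is adequate". The same section puts the drugs later washed out on the medication page, since all those "taken at Visit 1/Screening and for 90 days prior to Visit 1 and throughout the course of the study will be recorded".

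SAP 8.5 then classifies: "Prior medications are defined as any medications started and stopped prior to the day of first exposure to any study drug". A concomitant medication is one taken from the day of first exposure until 7 days after the last dose.

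**The concern.** A drug that qualifies for a year-only start has by definition been in use for more than 6 months, so a start on Day 1 cannot be true. Protocol 10.2 requires hypotensives to stop at least 28, 14 or 5 days (by class) before Visit 3, which is Day 1. Whenever the recorded year is the first-dose year, the rule therefore produces a start later than the recorded stop.

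Two outputs are at stake. First, the medication classes in SAP 8.5: a washed-out hypotensive fails the prior definition and, if the program classifies on start date alone, appears in the ocular concomitant-medication summary as though used on treatment. Second, the AE tables in SAP 10.1: AEs are collected from consent, so an event that came and went during washout with a partial onset date can be moved to Day 1.

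**Working it through.** The plan states no figure on this point, so the check applies the written rules to dates.

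**Year-only medication start (A.2.i).** Inputs: first dose 15 October 2020; 28-day washout, so stop 17 September 2020; true start 10 February 2020 (220 days of use, which exceeds 6 months); start recorded only as 2020.
- The year matches, so the imputed start is 15 October 2020.
- 15 October minus 17 September = 28 days: the start is 28 days after the stop.
- Prior requires a start before 15 October 2020. It fails.
- Concomitant: yes if only the start is read; no if the stop is also read, and then the drug is in neither class.

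This does not depend on the dates chosen. The imputed start equals the first-dose date and the stop lies before it, so start is always later than stop. Taking 730 consecutive first-dose dates from 1 January 2020, with stops 1 to 59 days earlier in the same year, gives 39,530 combinations. The start falls after the stop, and the drug fails the prior definition, in all of them.

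**Contrast.** With a true start in May 2018 recorded as 2018, the rule gives January 2018 and the drug is correctly prior. The defect is confined to starts in the first-dose year.

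**When it can arise.** Assume that more than 6 months means at least 184 days at the stop date. After a 28-day washout the true start must be at least 28 + 184 = 212 days before first dose and no earlier than 1 January. The number of possible start days is therefore the day of the year of first dose minus 212.

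| First dose (2020) | Day of year | Affected start days |
|---|---|---|
| 31 July (earliest) | 213 | 1 |
| 1 September | 245 | 33 |
| 1 October | 275 | 63 |
| 1 November | 306 | 94 |
| 1 December | 336 | 124 |
| 31 December | 366 | 154 |

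In 2021 the earliest date is 1 August. With shorter washouts the 2020 window opens earlier: 17 July for 14 days, 8 July for 5 days. On the planned calendar (first enrolment September 2020, last completion June 2021), first doses from September to December 2020 are exposed. The last Day 1 would be about 8 April 2021 (30 June minus 83 days). First doses from January to then are not exposed, because a year-only start must lie in an earlier year.

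**Unknown day (A.3.i).** Protocol Table 3 lets a CAI be used during washout if it is stopped 5 days before Visit 3. Suppose first dose is 20 October, the CAI stopped on 15 October, and the start is known only as October. The imputed start is 20 October, 5 days after the stop.

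**AE.** Suppose first dose is 20 October, resolution 8 October, and onset known only as October. The imputed onset is 20 October, which is Day 1 and 12 days after resolution. SAP 10.1 settles Day 1 onsets by comparing the time of onset with the time of first dose. The date rules impute no time, so that comparison has nothing to work with.

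**The case against.** The strongest defence is that the rules apply only where warranted. A drug with a known stop before first dose must have started before it, so its class needs no imputed start. The preamble also permits a better date, and the recorded year and stop remain visible in the listings. A careful programmer would avoid the error. That stands as mitigation, but both clauses are discretionary and neither refers to the stop date. For AEs, a more conservative date is usually read as one that counts the event as treatment-emergent, which would keep the error.

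It is also fair that the AE case is narrow. The year-only allowance covers medications, AE onset is to be recorded as a date, and screening runs only from Day -35 to Day -1. A missing day is more plausible than a missing month.

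Three stronger readings are tempting, and the documents do not support them.
- A reader might infer that a table of prior glaucoma therapy would be wrong. SAP 8.5 defines prior medications but specifies summaries only of concomitant ones, and SAP 8.3 does not list prior therapy among the baseline characteristics.
- A reader might infer that a false Day 1 start of a prohibited drug would remove subjects from the per-protocol population. Protocol 13.7 and SAP 8.2 rest on reported deviations and a masked sponsor review. Neither says that imputed dates are used.
- A reader might put a percentage on it. Spreading starts evenly over 5 years and taking 2 to 5 affected months gives 2/60 = 3% to 5/60 = 8% of long-term drugs. The documents give neither that spread, nor the share recorded by year alone, nor a last enrolment month. Ongoing drugs would also sit in the denominator although they are correctly concomitant under any start date.

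**Conclusion.** Wrong as written, and minor. The rule yields impossible date pairs from data that the protocol expressly accepts. Those pairs can misclassify washed-out drugs and, less often, AEs that resolved before dosing.

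It arises only when the partial start falls in the same year (or month) as first dose and the stop precedes first dose. For year-only starts after a 28-day washout, that means first doses from about August to December, given the 184-day reading of 6 months. The documents do not give the number of affected records or the actual first-dose dates.

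The primary IOP model does not use these dates, and no effect on the per-protocol population is shown. The possible effect is on medication classification, the concomitant-medication summary and treatment-emergent AE counts.

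**What to change.** Add to SAP 7.3.2.1 A: the first-dose date is imputed only when the stop date is missing, the record is ongoing, or the stop is on or after first dose. Otherwise the start is the earliest date consistent with the recorded parts. An imputed start never exceeds the stop date. Apply part B to partial stop dates first, so that there is a date to compare.

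In the examples above, the hypotensive gets 1 January 2020 and is prior, the CAI gets 1 October and starts before its stop, and the AE gets 1 October and is not treatment-emergent.

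Sending every unknown medication month to January is not needed. It would make a drug begun on treatment in that year look pre-existing. The cost is a few lines of SAP text and a small program change. No data collection changes.

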###### **B. Stop Dates**

- 1) If the year is unknown, then the date will not be imputed and will be assigned a missing value.
- 2) If the month is unknown, then assign 'December.'
- 3) If the day is unknown, then assign the last day of the month.

#### 7.3.2.2. Baseline

Except for specific analyses noted later (e.g., IOP), baseline values will be the last observation measured prior to dosing. If a repeat value is measured prior to dosing this value can be used for baseline.

#### 7.3.2.3. Missing Baseline Data

Every effort will be made to ensure that accurate baseline information on the subjects is collected. In the event that a subject is missing baseline information the subject will be included in the safety population for assessment of safety and excluded from the primary analyses. All baseline data will be observed cases, without imputation.

#### 7.3.2.4. Imputation Methods

Multiple imputation methods and single imputation methods (e.g., LOCF) will be utilized for sensitivity analyses that include repeating the primary analysis with the ITT population.

##### 7.3.2.4.1. Last Observation Carried Forward (LOCF)

Subjects with missing post-baseline efficacy data will be imputed using the LOCF method for the sensitivity analysis for all primary and secondary efficacy endpoints. For LOCF imputation, missing post-baseline efficacy data will be carried forward from the last non-missing post-baseline value for that endpoint. Baseline efficacy data will not be carried forward to any missing post-baseline value.

##### 7.3.2.4.2. Multiple Imputation

An alternative method of handling missing efficacy data in sensitivity analyses will be the method of multiple imputation. The pattern of missing observations in each treatment group will not influence the missing value estimation in the other because the imputation will be conducted independently for each treatment group. Missing data will be assumed to be missing at random (MAR).

For the imputation step, missing values will be separated into non-monotone missing values (i.e., intermittent missing values between completed assessments) and monotone missing values (i.e., missing values after the subject dropped out). SAS PROC MI procedure will sequentially estimate an imputation model for the IOP values at each post-baseline timepoint where IOP values are collected, separated between the treatment groups.

For the imputation of intermediate missing values, the missing IOP values in each data set will be filled in using the Markov-Chain Monte Carlo (MCMC) method with multiple chains and monotone imputing. A total number of imputations will be 100. The seed used for these imputations will be 2021.

Once the intermediate missing data are imputed, the monotone missing data will be imputed for all subjects with monotone regression. The dataset is the output dataset of the partial imputation. Since this dataset already has 100 imputed values at each visit, only one imputation will be performed.

Analysis timepoint results will be combined for overall inference to account for the uncertainty associated with the imputed values. This will be done using SAS PROC MIANALYZE.

### **7.3.3. Handling of Early Termination Visit Information**

In the event that a subject is terminated early from this study the early termination visit data for safety variables will be analyzed at the closest scheduled visit. If the closest visit has valid data, the early termination data will be assigned to the next available visit.

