9.4. Safety Assessments

Safety will be assessed at each visit by LogMAR VA, biomicroscopy, resting heart rate (HR)/blood pressure (BP), and AE collection. Ophthalmoscopy/dilated fundus examination and VF testing will be performed at Visit 1/Screening and Visit 6/Day 84. Safety/tolerability assessments at each visit will include grading of conjunctival hyperemia by the Investigator and subjective assessment of comfort/tolerability data by the subject. Ophthalmic assessments should be performed in the order in which they appear in the Schedule of Procedures (Table 2).

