9.4.6. Visual Field Testing

Automated perimetry will be performed at Visit 1/Screening and Visit 6/Day 84. The site should perform the automated perimetry assessments following the investigator's standard practices. If the VF performed at or within 90 days prior to Visit 1 does not meet study required parameters, it may be repeated (test should be prior to randomization at Visit 3/Qualification/Baseline/Day 1).

The preferred equipment for the VF is the Humphrey Perimeter using the full threshold 24-2 test with the SITA Standard or SITA Fast strategy. The same strategy used for the initial test should be used for any subsequent VF test. Visual field results should be reliable. Subjects with a functionally significant VF loss, defined as mean deviation greater than -12 dB or a central fixation point less than 5 dB in either eye, are excluded from the study. Other equipment may be used after approval by the Sponsor. Consult the Study Manual for specific details.

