10.4. Treatment Visits

These treatment visits (Visit 4/Day 15, Visit 5/Day 42, and Visit 6/Day 84), will be scheduled so that IOP can be taken at 8:00 AM, at 2 hours after the dosing of study medication at the clinical site (\sim 10:00 AM), and at 4:00 PM (each ± 30 minutes).

Subjects should be reminded before each visit not to dose in the morning before coming to the site and to bring their box containing all study medication materials (opened and unopened bottles/vials and pouches) to the study site for drug accountability/treatment compliance assessment. When the subject arrives, confirm that the previous day's evening dose of study medication *was* administered, and the morning dose of study medication *has not* been administered. Subjects who did not dose the evening before or who dosed prior to the morning visit MUST be rescheduled, even if the next appointment is out of window.

10.4.1. Visit 4/Day 15 ± 3

Procedures performed at Visit 4 include the following:

8 AM (± 30 minutes):

- AE assessment
- Concomitant medication review
- BCVA
- Grading conjunctival hyperemia
- Biomicroscopy
- IOP
- Drop instillation (should occur as close as possible to 15 minutes after IOP measurement, but not before 10 minutes after IOP measurement)
- Conduct drop comfort rating following instillation of study medication (≥ 10 minutes after the IOP measurement)

2 hours ± 30 minutes after drop instillation:

- AE assessment
- HR/BP
- Biomicroscopy
- IOP
- Blood collection for pharmacokinetics (PK) assessment (subset of subjects only)
- Compliance assessment (may be performed at any time during the visit)

4 PM (± 30 minutes):

- AE assessment
- Biomicroscopy
- IOP
- Study medication dispensing
- Study medication accountability (may be performed at any time during the visit)

10.4.2. Visit 5/Day 42 ± 3

8 AM (± 30 minutes):

- AE assessment
- Concomitant medication review
- BCVA
- Grading conjunctival hyperemia
- Biomicroscopy
- IOP
- Drop instillation (should occur as close as possible to 15 minutes after IOP measurement but not before 10 minutes after IOP measurement)
- Conduct drop comfort rating following instillation of study medication (≥ 10 minutes after the IOP measurement)

2 hours ± 30 minutes after drop instillation:

- AE assessment
- HR/BP
- Biomicroscopy
- IOP
- Compliance assessment (may be performed at any time during the visit)

4 PM (± 30 minutes):

- AE assessment
- Biomicroscopy
- IOP
- Study medication dispensing

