10.4.3. Visit 6/Last Day of Treatment (Day 84 ± 3)

At Visit 6, subjects will undergo final efficacy and safety assessments and rate the ocular tolerability of study medication.

Visit 6 procedures include the following:

8 AM (± 30 minutes):

- AE assessment
- Concomitant medication review
- Urine pregnancy test (females of childbearing potential only)
- BCVA
- Grading conjunctival hyperemia
- Biomicroscopy
- IOP
- Drop instillation (should occur as close as possible to 15 minutes after IOP measurement, but not before 10 minutes after IOP measurement)
- Conduct drop comfort rating following instillation of study medication (≥ 10 minutes after the IOP measurement)
- Visual field test (may be performed at any point in the visit prior to dilation for ophthalmoscopy)

2 hours ± 30 minutes after drop instillation:

- AE assessment
- HR/BP
- Biomicroscopy
- IOP
- Blood collection for PK assessment (subset of subjects only)
- Compliance assessment (may be performed at any time during the visit)

4 PM (± 30 minutes):

- AE assessment
- Biomicroscopy
- IOP
- Dilated ophthalmoscopy
- Study medication accountability (may be performed at any time during the visit)

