#### **10.4. Vital Signs**

Descriptive statistics of observed values will be presented for vital sign data by scheduled study visit, including systolic blood pressure (mm Hg), diastolic blood pressure (mm Hg), heart rate (beats/min) by treatment group for subjects in the Safety Population. Changes from baseline to each scheduled post-baseline visit will be presented.

All vital sign data by subject will be presented in a listing. Unscheduled visit results will not be summarized but will be included in patient data listings.

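### SAP 7.3.3 can file early-termination safety data under later visits, or visits where the test is not done, with no limit on distance and no check on dosing

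*SAP*

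**What the plan says.** SAP 7.3.3 covers subjects terminated early from the study. Its first step is that "the early termination visit data for safety variables will be analyzed at the closest scheduled visit". Its second is: "If the closest visit has valid data, the early termination data will be assigned to the next available visit". The section does not define *valid data* or *next available*, and gives no window or dosing condition.

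The remapped values then enter by-visit tables. SAP 10.4 states: "Descriptive statistics of observed values will be presented for vital sign data by scheduled study visit", and "Changes from baseline to each scheduled post-baseline visit will be presented". SAP 10.3 summarises the ophthalmic examinations by time point. Both sections leave unscheduled results out of the summaries, and no early-termination row is planned.

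On timing, Protocol 10.4.3 places HR/BP at Visit 6 in the block headed "2 hours ± 30 minutes after drop instillation"; Visits 4 and 5 follow the same pattern. Protocol 9.4 states: "Ophthalmoscopy/dilated fundus examination and VF testing will be performed at Visit 1/Screening and Visit 6/Day 84". Protocol 9.4.6 repeats this for perimetry.

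**The concern.** A by-visit safety table is read as a description of subjects at that visit. The second sentence of the rule moves data away from the visit that the first sentence has just identified as closest, and it always moves them forward in time. A Day 84 HR/BP row can therefore contain measurements taken weeks earlier, and nothing requires that they were taken at the post-dose time that defines the row.

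For assessments done after baseline only at Visit 6, the same rule can place an early leaver's only on-study result in a row for a visit at which nobody else was tested. That removes it from the one scheduled post-baseline summary.

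Ocular and systemic safety against timolol solution is part of the primary objective (SAP 4.1.1). The protocol introduction names decreased heart rate as a beta-blocker risk and postulates fewer systemic adverse events with the smaller drop. The HR/BP tables bear directly on that.

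**Working it through.** **Inputs.** Visit 3 is Day 1; Visits 4, 5 and 6 are Days 15, 42 and 84, each ± 3 days (Protocol 10.3.1 and 10.4, Table 2). HR/BP is measured at each of Visits 3 to 6. VF and dilated ophthalmoscopy are done at Visits 1 and 6 only. The mapping rule is SAP 7.3.3. No figure in the plan depends on this rule, so there is none to reproduce.

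**Assumptions.** Nominal visit days, and every visit before the exit day attended with valid data.

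**Step 1: midpoints between visits.** (1 + 15)/2 = 8; (15 + 42)/2 = 28.5; (42 + 84)/2 = 63.

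**Step 2: HR/BP.** Days early = nominal day of assigned visit − exit day.

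| Exit day | Closest visit | Already has data? | Reported as | Days early |
|---|---|---|---|---|
| 2–7 | 3 | yes | Day 15 | 8–13 |
| 9–14 | 4 | no | Day 15 | 1–6 |
| 16–28 | 4 | yes | Day 42 | 14–26 |
| 29–41 | 5 | no | Day 42 | 1–13 |
| 43–62 | 5 | yes | Day 84 | 22–41 |
| 64–83 | 6 | no | Day 84 | 1–20 |

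Days 8 and 63 are ties. Both go forward whichever way the tie is broken: Day 8 to Day 15 (7 days early) and Day 63 to Day 84 (21 days early).

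**Step 3: how often the shift is large.** It is at least 14 days for exit Days 16–28 (13 days), 43–63 (21) and 64–70 (7): 13 + 21 + 7 = 41 of the 82 possible exit days. Of these, 13 + 21 = 34 arise from the second sentence of the rule. It is at least 21 days for Days 16–21 (6) and 43–63 (21): 27 of 82. These are counts of calendar days, not of subjects.

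**Step 4: visit windows.** Visit 4 on Day 12 and exit on Day 13 gives 42 − 13 = 29 days. Visit 5 on Day 39 and exit on Day 40 gives 84 − 40 = 44 days.

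**Step 5: VF, three readings of the rule.**

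| Reading | Visit 3 | Visit 4 | Visit 5 | Visit 6 |
|---|---|---|---|---|
| *Valid data* judged per variable | exit Day 2–7 | 9–28 | 29–62 | 64–83 |
| *Valid data* judged per visit | never | up to 15 | 16–42 | later |
| Only visits where VF is scheduled count | never | never | never | all (1–82 days early) |

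On the per-variable reading, Day 8 ties between Visits 3 and 4, and Day 63 between Visits 5 and 6. Dilated ophthalmoscopy has the same schedule and maps the same way.

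**Step 6: dosing status.** Protocol 10.5 asks that the early-discontinuation visit repeat the Visit 6 procedures, which include drop instillation and HR/BP 2 hours later. It also allows a shortened visit. Protocol 7.3 places these procedures at the visit of withdrawal. A remapped value may therefore be on drug and post-dose, off drug, or undetermined. SAP 7.3.3 does not separate these cases.

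**Step 7: number affected.** No dropout rate is given. Assuming 2% to 15% early termination, 60 × 0.02 = 1.2 to 60 × 0.15 = 9 subjects per arm would be remapped, spread over all exit days.

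**The case against.** The strongest reply is that little rides on this. The tables are descriptive, with no hypothesis test. Clinically significant HR/BP changes are reported as adverse events (Protocol 9.5.3), and events leading to discontinuation have their own tables and listings (SAP 10.1, 10.2.3). All vital signs are listed by subject. For half of the possible exit days (41 of 82) the shift is under 14 days. On the third reading every early VF reaches Visit 6, so that part is an ambiguity and not an established loss of data. All of this stands and limits the weight of the point. It does not make the visit labels correct or settle which reading a programmer should use.

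A reader might infer more, in three ways that the documents do not support:

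- *That the remapped HR/BP values are off drug, so a drug effect is diluted.* No section says so, and the early-termination visit is meant to include instillation. The rule also covers leaving the study. Subjects who stop medication but keep attending, as Protocol 7.3 encourages, are not remapped.
- *That a mean dilution can be stated.* With an assumed effect of −5 bpm, 3 to 9 of 60 subjects all leaving on Day 43 to 62, all off drug and fully recovered, 3/60 × 5 = 0.25 and 9/60 × 5 = 0.75 bpm. Every one of those inputs is assumed.
- *That early-termination VF results contaminate baseline.* A Visit 3 label needs the per-variable reading and an exit in about the first week. Even then, SAP 7.3.2.2 fixes baseline as the last observation before dosing, so the result could carry a wrong label but not serve as the baseline value.

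**Conclusion.** The point holds as a defect in a stated rule. Under nominal days and attended earlier visits, HR/BP is reported 14 to 26 days early in the Day 42 row and 22 to 41 days early in the Day 84 row for the exit intervals shown, and up to 44 days early once the visit windows are used. Values of unspecified dosing status are mixed with true 2-hour post-dose values. On two of three readings, VF and dilated ophthalmoscopy results can be filed at Visits 4 or 5, where those tests are not scheduled, and miss the Visit 6 row.

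The case rests on mislabelling and on undefined terms that allow different tables from the same data. It does not rest on a demonstrated shift in any mean, which cannot be computed without a dropout rate. The consequences are confined to descriptive safety summaries; the primary IOP analysis and the baseline definition are unaffected. The rule should be corrected before unmasking.

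**What to change.** Replace the rule in SAP 7.3.3 as follows:

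- Show early-termination safety data in a separate *Early termination* row.
- Include them in a scheduled-visit row only if taken within that visit's ± 3-day window and, for HR/BP, 2 h ± 30 min after an on-site dose.
- Summarise VF and dilated ophthalmoscopy in one end-of-study row labelled *Visit 6 or early termination*. This pools results from different days, but the label says so, which a Day 84 label would not.
- Never assign data collected after the first dose to Visit 3.

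A row for the last on-treatment value of HR/BP is optional and not needed to cure the defect.

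Cost: a SAP wording change, one or two extra table rows, and slightly smaller n in the Day 42 and Day 84 rows. No study procedure changes and no data are lost.
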